2.3 Safety Objectives

The safety objectives will include evaluation of study drug administration, adverse events assessed by NCI Common Terminology Criteria for Adverse Events (CTCAE) v4.03, serious adverse events including deaths on study treatment.

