6.1 General Rules for Dose Modifications/Delays for KRd+Elotuzumab Induction

In the event of a possible drug-related toxicity, the investigator should, to the best of his/her ability, assess its relationship to each of the drugs within the regimen (carfilzomib, lenalidomide, dexamethasone, elotuzumab), or to the combination to the extent possible. Actions outlined in the sections below should be instituted for the agent(s) considered likely to be involved.

If the dose of one drug in the KRd+elotuzumab regimen is delayed, interrupted, or discontinued, the treatment with the other drugs may continue as scheduled. However, if elotuzumab is permanently discontinued, the subject should be removed from protocol-mandated treatment, and followed up per protocol (KRd may continue off protocol at the discretion of the investigator). If dexamethasone is delayed or discontinued during induction, the administration of elotuzumab should be at the discretion of the investigator and based on clinical judgment (i.e., risk of hypersensitivity).

Subjects experiencing a 28-day delay in elotuzumab due to an elotuzumab-related AE must be discontinued from protocol-mandated treatment and followed up per protocol.

While dose delays or interruptions are permitted, the start of each cycle cannot be delayed and is fixed relative to Cycle 1 Day 1 of induction. Adjustments to the Cycle 1 Day 1 anchored schedule should not be performed. Missed doses should be skipped, not delayed, as detailed in the rules in the sections below.

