8.7 Follow-up

For subjects who discontinue study treatment before relapse or PD, disease evaluations should continue to be performed until relapse or confirmed PD, death, start of a new anticancer treatment, withdrawal of consent to study participation, or until the criteria for the final analysis are met (Section 14.5.1) whichever occurs first. The schedule for disease evaluation should follow the schedule outlined during maintenance. Survival follow-up will occur every 3 months (+/- 30 days) from the last administration of protocol-directed therapy until death, lost to follow-up, or until the criteria for the final analysis are met (Section 14.5.1) and may be conducted via telephone. Any second primary malignancies discovered during long-term follow-up will be documented. Follow-up clinical information may also be obtained through chart reviews or other data sources (e.g. death registries).

The investigator is responsible for following the subject during the required follow-up period even if the subject lives elsewhere or has been released from his or her care and is being treated at another institution.

If the subject cannot be contacted following three attempted telephone calls over a period of 10 business days, the subject will be contacted in writing. Lost to follow-up is defined as four consecutive unsuccessful documented attempts (telephone and written) to contact the subject.

NOTE: in the event the criteria for the final analysis are met, and there are subjects who have not yet been discontinued from study treatment, subjects in follow-up will continue to be followed until all subjects have discontinued study treatment and completed the Safety Follow-up Visit (see above).

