- **Second Primary Malignancies:** In ELOQUENT-2, invasive second primary malignancies have been observed in 9% of patients treated with elotuzumab+Rd and 6% of patients treated with Rd. Skin cancer was reported in 4.4% and 2.8% of patients treated with elotuzumab+Rd and Rd treated patients, respectively.
- **Hepatotoxicity:** Elevations in liver enzymes (aspartate transaminase/alanine transaminase [AST/ALT] >3X UNL, total bilirubin >2 x UNL, and alkaline phosphatase <2 xULN) consistent with hepatotoxicity were reported in 2.5% and 0.6% of elotuzumab+Rd and Rd treated patients, respectively in the ELOQUENT-2 trial. Two patients experiencing hepatotoxicity were not able to continue treatment; however, 6 out of 8 patients had resolution and were able to continue treatment.
- **Interference with Determination of Complete Response:** Elotuzumab is a humanized IgG kappa monoclonal antibody that can be detected on both the serum protein electrophoresis (SPEP) and immunofixation (IFE) assays used for the clinical monitoring of endogenous M-protein. This interference can impact the determination of complete response and possibly relapse from complete response in patients with IgG kappa myeloma protein.

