12.3.3 SAEs

All SAEs, whether related to study treatment or not, including those thought to be associated with protocol-specified procedures, will be collected. SAEs will be reported after informed consent and continuing through 90 days after the discontinuation of all protocol mandated therapy. If the subject initiates subsequent anti-cancer therapy prior to 90 days after cessation of study treatment, the reporting period is through 60 days following cessation of study treatment or until the start of the subsequent anti-cancer therapy, whichever is later. Any SAE occurring after these time periods that is believed to be related to study drug(s) or protocol-specified procedure should also be reported.

It is the responsibility of the Sponsor-Investigator, investigators and the protocol team to ensure SAEs are reported according to the Code of Federal Regulations (CFR), GCP, the protocol guidelines, IRB, and FDA policy.

SAEs will be followed until clinical recovery is complete and laboratory tests have returned to baseline, until progression has been stabilized, or until there has been acceptable resolution of the event. This may at times cause the follow-up period for SAEs to be greater than 90 days. Similarly, the Sponsor-Investigator is responsible for following the subject during the required follow-up period even if the subject lives elsewhere or has been released from his or her care and is being treated under another service at LCI.

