14.1.3 Treatment Discontinuation Date

The date the investigator makes the decision to discontinue elotuzumab. See Section 9 for criteria for discontinuation of treatment.

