14.3.8 Safety Endpoints

Safety endpoints will include treatment administration (cumulative dose, dose intensity, and relative dose intensity—dose intensity as a percent of intended dose intensity), AEs, SAEs, and deaths while on study therapy.

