14.5.6 Safety Analysis

Incident rates for treatment-emergent adverse events, adverse events leading to study drug discontinuation, SAEs and deaths while on study therapy will be summarized. Treatment-emergent adverse events are defined as follows:

- An adverse event that occurs after treatment start that was not present at the time of treatment start; **OR**
- An adverse event that increases in severity after treatment start if the event was present at the time of treatment start.

Cumulative doses will be calculated for each subject (for elotuzumab, carfilzomib and lenalidomide) in both absolute terms and as a percent of expected cumulative dose (relative dose intensity). Cumulative dose and relative dose intensity will then be summarized for the study arm.

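### The safety death summary covers only deaths on study therapy, with no post-treatment window, and late second cancers judged unrelated have no planned summary

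*Combined protocol and SAP*

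**What the plan says.** **Deaths.** The limit appears at three levels. The safety objective in Section 2.3 covers "serious adverse events including deaths on study treatment". The endpoint in Section 14.3.8 is "AEs, SAEs, and deaths while on study therapy". The analysis in Section 14.5.6 says "SAEs and deaths while on study therapy will be summarized". None defines when a subject ceases to be on study therapy. The only treatment-end milestone in Section 14 is in 14.1.3: "The date the investigator makes the decision to discontinue elotuzumab". Section 6.1 links that decision to the end of treatment: "if elotuzumab is permanently discontinued, the subject should be removed from protocol-mandated treatment". Section 6.2 says the same for maintenance.

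**Collection.** SAE reporting runs from consent, "continuing through 90 days after the discontinuation of all protocol mandated therapy" (Section 12.3.3). If subsequent anti-cancer therapy starts sooner, the window ends at 60 days or at the start of that therapy, whichever is later. An SAE believed related remains reportable after the window.

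**Second cancers.** Section 10.1.9 reports for the phase III trial of elotuzumab with lenalidomide and dexamethasone (Rd) that "invasive second primary malignancies have been observed in 9% of patients treated with elotuzumab+Rd and 6% of patients treated with Rd". Section 10.3.4 carries a similar warning for lenalidomide. Section 12.1.4 requires cancer to be handled as an SAE. For later cases Section 8.7 says: "Any second primary malignancies discovered during long-term follow-up will be documented". Section 14 names no endpoint or summary for them.

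**The concern.** The period in which deaths are summarised is shorter than the period in which serious events are collected, and its end can be set by toxicity. Section 9.1 lists unacceptable adverse events and intercurrent illness as reasons to stop treatment. Sections 6.1 and 6.2 require discontinuation after a 28-day elotuzumab delay caused by a related event. Whether a death is counted can therefore depend on the toxicity that led to it. A decision to stop made before the death can remove it from the summary, and nothing in the rule works in the other direction.

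Mortality associated with treatment is a central safety result for a single-arm study of a four-drug combination, and there is no concurrent arm in which the same rule would apply. For second cancers, whether a late case is counted depends on a judgement of relatedness that is hard to make in an individual subject.

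**Working it through.** The plan gives no figure here to reproduce. The check is to follow one type of event through each planned output, and then to ask what can be said about size.

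**A. Subject stops for toxicity and dies of it two weeks later, with no new therapy**

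1. Death summary (14.3.8, 14.5.6): excluded, if on study therapy ends at or near the decision in 14.1.3.
2. SAE collection (12.1.4, 12.3.3): captured, since a fatal event is serious and day 14 is inside the window.
3. SAE rate (14.5.6): probably included. The sentence can also be read as limiting SAEs, as well as deaths, to the time on therapy. The treatment-emergent definition has no end date, but it does not settle the reading.
4. Adverse events leading to discontinuation (14.5.6): the toxicity is counted. The plan does not say that a later fatal outcome is shown there.
5. Overall survival (14.3.3): counted, all causes together.
6. Disposition (14.5.2): counted as a death, with no cause or attribution specified.

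The event reaches several outputs. None is specified to show post-treatment deaths by timing, cause and relatedness.

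**B. Second primary malignancy**

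1. On treatment or within the SAE window: an SAE (12.1.4, 12.3.3).
2. After the window and believed related: still a reportable SAE (12.3.3).
3. After the window and judged unrelated: documented (8.7), with no planned summary. Follow-up can run until surviving subjects have been on study for at least 5 years (14.5.1).

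**C. Scale only**

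Inputs: n = 40 (14.2); fatal infection 2.5% and invasive second malignancy 9% with elotuzumab+Rd (10.1.9). Assumption: those rates carry over to this trial.

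- Fatal infections expected: 40 × 0.025 = 1.0.
- Weight of one death: 1/40 = 2.5 percentage points. The Clopper-Pearson 95% upper limit is 13.2% for 1/40 and 8.8% for 0/40, where 1 − 0.025^(1/40) = 0.088.
- Second malignancies expected: 40 × 0.09 = 3.6; chance of at least one: 1 − 0.91^40 = 0.977.

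These describe all such events, not the ones left out. The share of second malignancies that is both late and judged unrelated, s, is not in the documents. Expected unsummarised cases are 3.6 × s, and the rate left in the SAE summary is 9% × (1 − s):

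- s = 25%: 0.9 cases; 6.75%
- s = 50%: 1.8 cases; 4.5%
- s = 75%: 2.7 cases; 2.25%

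The documents give no corresponding share for deaths after stopping.

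**The case against.** The strongest reply is that the data are safe. A fatal toxicity after stopping is collected as an SAE, an SAE rate is planned, and every known death enters overall survival and disposition. That stands. A reader might infer that such deaths go unreported, and the documents do not support that. The gap is that overall survival mixes progression with toxicity, disposition specifies no cause, and an SAE rate does not separate fatal events.

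Second, a reader might take it as stated that study therapy ends on the date elotuzumab is stopped. Sections 14.3.8 and 14.5.6 do not cite 14.1.3. The link is a reasonable inference from 14.1.3 with 6.1 and 6.2, because no other end point is offered, but it remains an inference. A subject who dies while drugs are held, with no decision to discontinue, is arguably still on therapy and counted.

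Third, a reader might infer that every second cancer found after the SAE window enters no safety rate. That is too broad. Maintenance continues until relapse or progression, so the window covers all of treatment and a period beyond it, and later cases believed related remain reportable. Only late cases judged unrelated clearly lack a summary.

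Fourth, the expected counts do not measure the defect. This also stands. In particular, moving a death rate from 2.5% to 0% would require the one expected fatal infection to fall after stopping, and nothing in the documents says it would.

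**Conclusion.** The point holds as a gap in the safety reporting plan. The death summary stops at an undefined end of therapy, that end can be brought on by toxicity, and the resulting error can only lower the reported count. The conclusion rests on the plain reading that a subject is no longer on study therapy once protocol treatment has been discontinued.

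The number of deaths or second cancers affected cannot be derived from the documents; the figures above show only that single events matter with 40 subjects. The second-malignancy gap is secondary and confined to late cases judged unrelated. The primary endpoint and its decision rule are untouched.

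**What to change.** In Sections 14.3.8 and 14.5.6, with Section 2.3 aligned:

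- Summarise all deaths from Cycle 1 Day 1 through the Section 12.3.3 window: 90 days after the last administered protocol therapy or, if subsequent anti-cancer therapy starts earlier, 60 days or the start of that therapy, whichever is later. Add any later death believed related. A flat 90 days would not match the collection window and would bring in more deaths on subsequent therapy.
- Tabulate these deaths by timing (on treatment, within 30 days of last dose, later), cause and attribution. Anchor timing to the actual last dose, not to the decision date in 14.1.3.
- State whether the on-therapy limit in the 14.5.6 sentence applies to SAEs.
- Add a count and listing of all second primary malignancies from Cycle 1 Day 1 to the final analysis. Note that late ascertainment is passive: Section 8.7 records those discovered, survival contact may be by telephone, and Section 9.2 ends data collection for subjects off study. For that reason, and with 40 subjects, a competing-risk cumulative incidence is not needed.

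The cost is a wording change and two extra tables, mainly from data already collected. The reported death count may be slightly higher. No visit, dose or treatment rule changes.

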14.5.7 Interim Analysis

No pre-specified interim analyses are planned for this study.

15. STUDY COMPLETION OR TERMINATION

15.1 Completion

The study will be considered complete when one or more of the following conditions is met:

- All subjects have died and/or are withdrawn from the study
- All subjects have discontinued from the study
- The IRB, FDA, LCI DSMC, or Sponsor-Investigator discontinues the study because of safety considerations
- The Sponsor-Investigator defines an administrative or clinical cut-off date

15.2 Termination

The study will be terminated when one or more of the following conditions occur:

- If risk-benefit ratio becomes unacceptable owing to, for example,
 - Safety findings from this study (e.g. SAEs)
 - Results of any interim analysis

- Results of parallel clinical studies
- Results of parallel animal studies (e.g. toxicity, teratogenicity, carcinogenicity or reproduction toxicity).
- If the study conduct (e.g. recruitment rate; drop-out rate; data quality; protocol compliance) does not suggest a proper completion of the trial within a reasonable time frame.
- The Sponsor-Investigator has decided to close the trial at any site and at any time

For any of the above closures, the following applies:

- Closures should occur only after consultation between involved parties.
- All affected institutions must be informed as applicable according to local law.
- In case of a partial study closure, ongoing subjects, including those in follow-up, must be taken care of in an ethical manner.

16. STUDY MANAGEMENT

16.1 IRB Approval

The final study protocol and the final version of the informed consent form(s) must be approved in writing by the Sponsor IRB.

The Sponsor-Investigator is responsible for informing the Sponsor IRB of any amendment to the protocol in accordance with local requirements. The protocol must be re-approved by the IRB annually, as local regulations require.

16.2 Informed Consent

Before recruitment and enrollment onto this study, the subject will be given a full explanation of the study and will be given the opportunity to review the consent form. Prior to a subject's participation in the trial, the written informed consent form should be signed and personally dated by the subject and by the person who conducted the informed consent discussion.

16.3 Protocol Adherence

Except for an emergency situation in which proper care for the protection, safety, and well-being of the study subject requires alternative treatment, the study shall be conducted exactly as described in the approved protocol.

16.4 Changes to the Protocol and/or Informed Consent

16.4.1 Amendments to the Protocol

If it is necessary for the study protocol to be amended and/or the informed consent revised, the amendment or a new version of the study protocol (amended protocol) and/or the revised informed consent must be approved by the Sponsor-Investigator, funding company(ies) (if required by the contract(s), the FDA and the Sponsor IRB.

16.4.2 Emergency Modification

The Investigators may implement a deviation from, or a change of, the protocol to eliminate an immediate hazard(s) to the trial subjects without prior approval from applicable agencies. As soon as possible, the implemented deviation or change, the reasons for it and if appropriate the proposed protocol amendment should be submitted to the appropriate agencies. Any deviations from the protocol must be explained and documented by the investigator.

16.5 Other Protocol Deviations

If a deviation occurs, the event should be reported to the Sponsor-Investigator via entry in the CTMS no later than 10 business days after awareness.

Protocol deviations that, in the Investigator's judgment, potentially caused harm to participants or others or indicates that the participants or others are at an increased risk of harm, or has adversely impacted data integrity will be reported promptly to the Sponsor-Investigator and IRB per IRB reporting requirements.

NOTE: Planned protocol deviations will be submitted to the FDA for prior approval only if the deviation affects the scientific validity of the study and/or the rights, safety, or welfare of subjects.

16.6 Retention of Records

Essential documentation (e.g. AEs, records of study drug receipt and dispensation), including all IRB correspondence, will be retained for at least 2 years after the investigation is completed. Documentation will be readily available upon request.

16.7 Ethical and Legal Conduct of the Study

The procedures set out in this protocol, pertaining to the conduct, evaluation, and documentation of this study, are designed to ensure that the Investigator abide by GCP guidelines. The study will also be carried out in full conformity with Regulations for the Protection of Human Subjects of Research codified in 45 CFR Part 46, 21 CFR Part 50, 21 CFR Part 56, and/or the ICH E6 and in keeping with applicable local law(s) and regulation(s).

Documented approval from appropriate agencies (e.g. DSMC, IRB, FDA) will be obtained for all participating centers before the start of the study, according to GCP, local laws, regulations and organizations.

Strict adherence to all specifications laid down in this protocol is required for all aspects of study conduct; the investigators may not modify or alter the procedures described in this protocol.

The Sponsor-Investigator is responsible for the conduct of the clinical trial at the sites in accordance with Title 21 of the CFR and/or the Declaration of Helsinki. The Sponsor-Investigator is responsible for overseeing the treatment of all study subjects. The Sponsor-Investigator must assure that all study site personnel, including sub-investigators and other

study staff members, adhere to the study protocol and all applicable regulations and guidelines regarding clinical trials both during and after study completion.

The Sponsor-Investigator will be responsible for assuring that all the required data will be collected and properly documented.

16.8 Confidentiality of Records

All records identifying the subject will be kept confidential and, to the extent permitted by the applicable laws and/or regulations, will not be made publicly available.

16.9 Compliance with ClinicalTrials.gov

The Sponsor-Investigator is solely responsible for determining whether the trial and its results are subject to the requirements for submission to ClinicalTrials.gov (<http://www.clinicaltrials.gov>).

18. APPENDICES

18.1 Appendix A: ECOG Performance Status

Grade	Description
0	Normal activity. Fully active, able to carry on all pre-disease performance without restriction.
1	Symptoms, but ambulatory. Restricted in physically strenuous activity, but ambulatory and able to carry out work of a light or sedentary nature (e.g., light housework, office work).
2	In bed <50% of the time. Capable of only limited self-care, confined to bed or chair more than 50% of waking hours.
3	In bed >50% of the time. Capable of only limited self-care, confined to bed or chair more than 50% of waking hours.
4	100% bedridden. Completely disabled. Cannot carry on any self-care. Totally confined to bed or chair.
5	Dead.
Reference: Oken MM, Creech RH, Horney RH et al. Toxicity and Response Criteria of the Eastern Cooperative Oncology Group. Am J Clin Oncol 1982; 5:649-655.	

18.2 Appendix B: Cockcroft-Gault Equation

$$\text{Female CrCl} = \frac{(140 - \text{age in years}) \times \text{weight in kg} \times 0.85}{72 \times \text{serum creatinine in mg/dL}}$$

$$\text{Male CrCl} = \frac{(140 - \text{age in years}) \times \text{weight in kg} \times 1.00}{72 \times \text{serum creatinine in mg/dL}}$$

